4.3. Secondary Endpoints Analysis

4.3.1. Analysis of PK/PD

Serum concentration will be listed over time for each participant. All serum concentrations below the lowest quantifiable sample concentration of the assay (BQL) or missing data will be labeled as such in the concentration data listings.

Due to the early termination of the study and the limited sample size of enrolled participants, there will be no PK parameters outputs.

Absolute values, changes from Baseline, and percent change from Baseline of PD parameters (serum total and free properdin concentrations and CAP activity) will be listed over time for each participant.

4.3.2. Analysis of SCD Biomarkers

Absolute value, change from Baseline, and percent change from Baseline in biomarkers, including Ba, C3a, C4a, C5a, sC5B9, LDH, bilirubin (total, direct and indirect), reticulocytes (absolute and percent), haptoglobin and hemopexin will be listed over time for each participant.

4.3.3. Analysis of Immunogenicity

Baseline is defined as the last nonmissing antidrug antibody (ADA) signal obtained on or before the first study intervention administration.

For assessment of immunogenicity, the signal of ADAs will be categorized as positive or negative. Additionally, following confirmation of positive ADAs, samples will be further categorized into ADA response categories and will be assessed for ADA titer over time. ADA categories are defined as follows:

- **ADA negative:** An ADA-negative signal in the ADA assay at all timepoints collected for ADA analysis
- **ADA positive:** An ADA-positive signal in the ADA assay at any timepoint collected for ADA analysis

Participants who are ADA positive may be further categorized into ADA response categories as follows:

- **Pre-existing immunoreactivity:** An ADA-positive response with either of the following 2 conditions met:

- ADA-positive response at Baseline with all post-first-dose ADA results negative
OR
- ADA-positive response at Baseline with all post-first-dose ADA responses < 4-fold over the baseline titer level
- **Treatment-emergent ADA responses:** An ADA-positive response post-first dose when baseline results are negative or missing
- **Treatment-boosted ADA responses:** An ADA-positive response post-first dose that is ≥ 4 -fold over the baseline titer level when the baseline result is positive

4.4. Exploratory Endpoints Analysis

Absolute value, change from Baseline, and percent change from Baseline in the markers of VOC, including hemopexin and nitric oxide, will be listed over time for each participant.

SCD-related pain crises (VOC) are defined as acute episodes of pain with no medically determined cause other than a VOC event that results in a medical facility visit and treatment with either oral or parenteral narcotic agents or with a parenteral nonsteroidal anti-inflammatory drug. Uncomplicated VOCs are defined as no occurrence of any other SCD complication during the VOC episode. Complicated VOCs are defined as the presence of a diagnosis of other SCD complications during the VOC episode. Acute chest syndrome, hepatic sequestration, splenic sequestration, and priapism are considered VOC events in this study.

The following information of VOC assessments will be listed:

- VOCs leading to a healthcare visit
- Start and end date of VOC
- Complicated VOC or uncomplicated VOC
- If complicated VOC, the complicated VOC categories will be listed (acute chest syndrome, hepatic sequestration, splenic sequestration, priapism or other)
- Location of pain
- Tiredness during pain crisis
- Intensity of pain
- Medication Taken
- VOC exacerbate (if yes, reporting to AE)

4.5. Changes to Protocol-Planned Analyses

Due to the early termination of the study and limited enrolled participants, data will only be listed. Applicable changes from Protocol Amendment 1.0 are as follows:

- The interim analyses have been removed

- The Cohort 3 will not be initiated and have been removed
- Analysis sets have been removed except for Enrolled Set, all analyses will be based on the Enrolled Set
- Analyses of PK parameters have been removed
- Summary descriptive statistics will not be provided
- Outlier analyses of ECG have been removed
- Inflammatory biomarkers and cell adhesion biomarkers have been removed from the analysis of VOC-related biomarkers
- Visit windows have been removed

5. SAMPLE SIZE DETERMINATION

Twelve participants were planned to be enrolled in each of Cohorts 1 and 2. In participants with stable SCD, hemoglobin level is unlikely to change. The sample size was determined based on a targeted hemoglobin change from Baseline to exclude 0 g/dL with a lower 2-sided 95% confidence bound. Assuming a standard deviation of 1 g/dL, a sample size of 12 participants can provide 88% power to detect a change from Baseline of 1 g/dL with a 2-sided significance level of 0.05. In Optional Cohort 3, 6 participants were planned to be enrolled to define the exposure/response relationship of ALXN1820 by combining Cohorts 1, 2, and 3 data using a PK/PD modeling approach. The Optional Cohort 3 sample size was not determined for power purposes.

After the decision of the study early termination, the Cohort 3 will not be enrolled.

6. SUPPORTING DOCUMENTATION

6.1. Technical Specifications for Derived Variables

Adverse Events

The analysis of AE is described in detail in Section **Error! Reference source not found.**

TEAEs are events with start dates and start times on or after the date and time of the first dose of study intervention and up to 100 days after the last dose of the study intervention. If the start date of an AE is partially or completely missing and the end (stop) date and time of the AE do not indicate that it occurred prior to the first dose, then the determination of treatment-emergent status will be based on the following:

- If the start year is after the year of the first study intervention dose, then the AE is treatment emergent; else,
- If the start year is the same as the year of the first study intervention dose and
 - the start month is missing, then the AE is treatment emergent; else if
 - the start month is present and is the same or after the month of the first study intervention dose, then the AE is treatment emergent; else,
- If the start date is completely missing, then the AE is treatment emergent.

All other AEs are considered pretreatment AEs.

If the relationship to study intervention is missing for TEAEs, then the relationship will be counted as related to study intervention for the listing tables. Missing severity for TEAEs will be counted as Grade 3.

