Cohort 1 and Cohort 2 will run in parallel, and patients will be randomized 1:1 to either of the cohorts on determination of eligibility. The decision to initiate Optional Cohort 3 will be made at Alexion's discretion and will be based on analysis of PK/PD and safety after at least 8 patients from Cohorts 1 and 2 (4 from each cohort) have enrolled. Furthermore, enrollment of Optional Cohort 3 will start after Cohorts 1 and 2 are fully enrolled. Each cohort will be stratified to ensure patients with SCD who are treated with a stable dose of hydroxyurea and patients with SCD who are not currently treated with hydroxyurea are included. The Treatment Period will be 12 weeks for Cohorts 1 and 2, and 6 weeks for Cohort 3. For patients who were previously treated with hydroxyurea but are not currently on hydroxyurea, treatment must have been stopped at least 30 days prior to providing informed consent.

At Alexion's discretion, and after consultation with the Data Monitoring Committee (DMC), additional participants with SCD may be enrolled as replacement participants if a participant discontinues during the Dosing Period for reasons other than drug-related adverse events (AEs).

Disclosure Statement This is an open-label, parallel group intervention study with up to 3 treatment arms.

Number of Participants:

Up to 30 adult patients with SCD (HbSS and HbSβ⁰-thalassemia) will be enrolled in up to 3 cohorts and will receive multiple open-label SC doses of ALXN1820. The cohorts will enroll both patients with SCD who are being treated with a stable dose of hydroxyurea and patients with SCD who are not currently treated with hydroxyurea. For patients who were previously treated with but are not currently on hydroxyurea, treatment must have been stopped at least 30 days prior to providing informed consent.

Intervention Groups and Duration:

The planned study duration is approximately 38 weeks for Cohorts 1 and 2: up to 56 days (8 weeks) for Screening, 84 days (12 weeks) for the Treatment Period, and 126 days (18 weeks) for the Follow-up Period. Patients will attend outpatient visits during the Treatment and Follow-

up Period with the option to stay at the inpatient facility. The end of study (EOS) for each individual patient is anticipated to be Day 211 (210 days) or the timepoint at which complement activity has returned to a normal range or 80% of baseline if later than Day 211.

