8.3.1. Time Period and Frequency for Collecting AE and SAE Information

All AEs and SAEs will be collected from the signing of the ICF until the last follow-up visit.

All SAEs will be recorded and reported to Alexion or the designee immediately and under no circumstance should this exceed 24 hours, as indicated in Section 10.3. The Investigator will submit any updated SAE data to Alexion within 24 hours of the date the investigational site became aware of the event.

Investigators are not obligated to actively seek AE or SAE data after conclusion of the study participation. However, if the Investigator learns of any SAE, including a death, at any time after a participant has been discharged from the study, and he/she considers the event to be reasonably related to the study intervention or study participation, the Investigator must promptly notify Alexion.

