10.3.1. Definition of AE

AE Definition

- An AE is any untoward medical occurrence in a participant or clinical investigation participant administered a pharmaceutical product and which does not necessarily have to have a causal relationship with this treatment (ICH E2A).
- **Note:** An AE can therefore be any unfavorable and unintended sign (including an abnormal laboratory finding), symptom, or disease [new or exacerbated] temporally associated with the use of the study intervention, whether or not considered related to the study intervention.

Events Meeting the AE Definition

- Any abnormal laboratory test results (hematology, clinical chemistry, or urinalysis) or other safety assessments (eg, ECG, radiological scans, vital signs measurements), including those that worsen from baseline, considered clinically significant in the medical and scientific judgment of the Investigator (ie, not related to progression of underlying disease).
- Exacerbation of a chronic or intermittent pre-existing condition including either an increase in frequency and/or intensity of the condition.
- New conditions detected or diagnosed after study intervention administration even though it may have been present before the start of the study.
- Signs, symptoms, or the clinical sequelae of a suspected drug-drug interaction.
- Signs, symptoms, or the clinical sequelae of a suspected overdose of either study intervention or a concomitant medication. Overdose per se will not be reported as an AE/SAE unless it is an intentional overdose taken with possible suicidal/self-harming intent. Such overdoses should be reported regardless of sequelae.

Events Not Meeting the AE Definition

- Medical or surgical procedure (eg, endoscopy, appendectomy): The condition that leads to the procedure is the AE. Situations in which an untoward medical occurrence did not occur (eg, hospitalization for elective surgery if planned before the signing the ICF, admissions for social reasons or for convenience).
- Anticipated day-to-day fluctuations of pre-existing disease(s) or condition(s) present or detected at the start of the study that do not worsen.
- A medication error (including intentional misuse, abuse, and overdose of the product) or use other than what is defined in the protocol is not considered an AE unless there is an untoward medical occurrence as a result of a medication error.

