 - Related: There is a reasonable possibility the study intervention caused the AE.
 - The AE has a temporal relationship to the administration of the study intervention.
 - The event does not have a likely alternative etiology.
 - The event corresponds with the known pharmaceutical profile of the study intervention.
 - There is improvement on discontinuation and/or reappearance on rechallenge.
- The Investigator will use clinical judgment to determine the relationship.
- Alternative causes, such as underlying disease(s), concomitant therapy, and other risk factors, as well as the temporal relationship of the event to study intervention administration will be considered and investigated.
- The Investigator will also consult the IB and/or Product Information, for marketed products, in his/her assessment.
- For each AE/SAE, the Investigator **must** document in the medical notes that they have reviewed the AE/SAE and has provided an assessment of causality.
- There may be situations in which an SAE has occurred, and the Investigator has minimal information to include in the initial report to Alexion. However, it is very important that the Investigator always make an assessment of causality for every event before the initial transmission of the SAE data to Alexion.
- The Investigator may change his/her opinion of causality in light of follow-up information and send an SAE follow-up report with the updated causality assessment.
- The causality assessment is one of the criteria used when determining regulatory reporting requirements.

Follow-up of AEs and SAEs

- The Investigator is obligated to perform or arrange for the conduct of supplemental measurements and/or evaluations as medically indicated or as requested by Alexion to elucidate the nature and/or causality of the AE or SAE as fully as possible. This may include additional laboratory tests or investigations, histopathological examinations, or consultation with other health care professionals.
- If a participant dies during participation in the study or during a recognized follow-up period, the Investigator will provide the Sponsor or designee with a copy of any post-mortem findings including histopathology.
- New or updated information will be recorded in the originally completed eCRF.

Follow-up of AEs and SAEs

- The Investigator will submit any updated SAE data to Alexion within 24 hours of receipt of the information.

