1.1. Objectives, Endpoints, and Estimands

The objectives and endpoints of ALXN 1820-SCD-201 are summarized in [Table 1](#)

Table 1: Objectives and Endpoints

Objectives	Endpoints
Primary	
To assess the safety and tolerability of ALXN1820 SC in participants with SCD	Safety assessed by incidence of TEAEs and SAEs, physical examination, vital sign measurements, clinical laboratory, and electrocardiogram results through Day 211 (Cohorts 1 and 2)
Secondary	
To assess the multiple-dose PK of ALXN1820 SC	Serum ALXN1820 multiple-dose PK profiles through Day 211 (Cohorts 1 and 2)
To assess the PD effects of ALXN1820 SC	Change in serum concentrations of total and free properdin over time through Day 211 (Cohorts 1 and 2) Change in CAP activity using the Wieslab AP assay through Day 211 (Cohorts 1 and 2)
To assess the effect of ALXN1820 on complement biomarkers	Change from Baseline in complement biomarkers through Week 12 (Cohorts 1 and 2)
To assess the effect of ALXN1820 on hemolysis biomarkers	Change from Baseline in hemoglobin levels at Week 12 (Cohorts 1 and 2) Change from Baseline in hemolysis markers (e.g., lactate dehydrogenase, reticulocytes, and bilirubin and hemopexin) at Week 12 (Cohorts 1 and 2)
To assess the immunogenicity of ALXN1820 SC	Incidence of ADAs to ALXN1820 through Day 211 (Cohorts 1 and 2)
Exploratory	
To explore the effect of ALXN1820 on VOC markers	Change from Baseline in VOC-related biomarkers through Week 12 (Cohorts 1 and 2)

Table 1: Objectives and Endpoints

Objectives	Endpoints
To explore the clinical efficacy of ALXN1820 SC in SCD	VOC events (rate of VOC, time to first VOC) through Week 12 (Cohorts 1 and 2)

Abbreviations: ADA = antidrug antibody; AP = alternative pathway; CAP = complement alternative pathway; PD = pharmacodynamic; PK = pharmacokinetic(s); SAE = serious adverse event; SC = subcutaneous; SCD = sickle cell disease; TEAE = treatment-emergent adverse event; VOC = vaso-occlusive crisis.
 Note: Estimand is not applicable.

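### The SAP's TEAE definition has no worsening criterion, so a Screening-onset AE that worsens on drug under its original record is flagged pretreatment in the AE listing

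*SAP*

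**What the plan says.** - SAP 6.1 holds the only operative definition; the protocol uses the term TEAE in its primary endpoint without defining it. The rule begins "TEAEs are events with start dates and start times on or after the date and time of the first dose of study intervention" and runs "up to 100 days after the last dose of the study intervention". After the rules for partial dates comes the residual clause: "All other AEs are considered pretreatment AEs". Grade change and seriousness are not criteria.
- The same section sets two defaults that apply to TEAEs only: a missing relationship is counted as related, and a missing severity as Grade 3.
- Protocol 8.3.1: "All AEs and SAEs will be collected from the signing of the ICF until the last follow-up visit". The Synopsis allows "up to 56 days (8 weeks) for Screening".
- Protocol 10.3.1 includes among events meeting the AE definition: "Exacerbation of a chronic or intermittent pre-existing condition including either an increase in frequency and/or intensity of the condition". Protocol 10.3.3, under follow-up of AEs, says: "New or updated information will be recorded in the originally completed eCRF". Administrative Change Letter #2 has VOCs reported as AEs when they are exacerbated from Day 1.
- The primary endpoint in SAP 1.1 opens with "Safety assessed by incidence of TEAEs and SAEs".
- Under SAP 1, 4.2.1 and 4.5, the final output is listings without summary statistics. Every AE is listed, and TEAE status is indicated on that listing. SAP 1.2 reports 2 participants enrolled at early termination.

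**The concern.** A TEAE definition normally covers two situations: an event that starts after dosing, and an event already present that gets worse after dosing. SAP 6.1 covers only the first. The second can occur here. Collection starts at consent, vaccines may be given during Screening, and inclusion criterion 6 requires 1 to 10 VOCs in the past 12 months, so some AEs may still be open on Day 1.

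This is the first exposure of patients with SCD to the drug (protocol 2.3.1), and there is no untreated arm for comparison. Worsening on drug is information that the safety output should identify as such. Because incidence tables have been dropped, the TEAE flag is the only form in which the SAP delivers the TEAE part of its primary endpoint. A wrong flag therefore matters somewhat more than it would beside full tables.

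**Working it through.** The point turns on a definition, and the plan states no figure to reproduce. The check applies the SAP 6.1 rule to test cases with complete dates, and then bounds how often the problem could arise for VOC.

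**Step 1. Apply the rule.** First dose is Day 1 and last dose is Day 85 (both cohorts, protocol Tables 3 and 4). The window closes on Day 85 + 100 = Day 185.

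- AE starts Day -20 and worsens on Day 30, kept as one record: the start precedes Day 1, so it is pretreatment.
- Same worsening on Day 30, entered as a new AE: the start is Day 30, so it is a TEAE.

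The same clinical course receives opposite labels depending on how the site records it.

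**Step 2. Do the documents settle how it is recorded?**

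- Protocol 10.3.1 treats an exacerbation as an AE in its own right, which points to a new record.
- Protocol 10.3.3 sends updated information to the existing eCRF, which points to one record. It does not mention grade changes or start dates.
- Letter #2 makes exacerbation from Day 1 the trigger for reporting a VOC as an AE, but does not say whether the start date is the VOC onset or the exacerbation.

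None of these says which start date a worsened event carries. The eCRF completion guideline is not among the documents.

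**Step 3. What does the label change?**

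- The TEAE flag on the AE listing.
- The two missing-data defaults, which a pretreatment event does not receive.
- How the row reads. SAP 4.2.1 names severity but no date of worsening, so an event that reached Grade 3 on drug could appear as a Grade 3 pretreatment AE. Detailed listing specifications sit in a separate Data Presentation Plan that was not available, so this is a possibility only.

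**Step 4. Bound the frequency for VOC.** Inputs: 1 to 10 VOCs per year (inclusion 6); duration 3 to 7 days, an assumption because the documents give none; 2 participants (SAP 1.2). With onsets at a constant rate,

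P(VOC open at first dose) = 1 − exp(−rate × duration / 365)

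- Low end: 1 − exp(−1 × 3/365) = 1 − exp(−0.0082) = 0.8%
- High end: 1 − exp(−10 × 7/365) = 1 − exp(−0.1918) = 17.5%
- Expected number among 2 participants: 2 × 0.0082 = 0.02 to 2 × 0.1745 = 0.35

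This is an upper bound for VOC, since only a crisis that worsens after dosing and stays in one record is affected. Other Screening-onset AEs would add to it; the documents give no rate for them.

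**The case against.** The strongest reply is that nothing is hidden. Every AE is listed for each participant, on the Enrolled Set and with no TEAE filter, beside its grade, relationship, seriousness and a VOC-exacerbation item. SAP 4.4 separately lists each VOC with its dates, pain intensity, complication category and exacerbation status. Laboratory values are listed by visit with change from Baseline, and CTCAE grades are listed where applicable. An event that becomes serious still counts in the SAE component whatever its TEAE flag. If sites enter worsening as a new AE, the existing rule already works. SAP 6.1 also leans against the drug elsewhere: a completely missing start date makes an AE treatment-emergent unless its end date shows that it occurred before the first dose.

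Most of this stands. A reader might infer that a worsened Screening AE drops out of the primary safety endpoint, or that a signal is removed in the drug's favour. The documents do not support that: no TEAE count is planned for it to leave, and the row stays in the listing. Nor is it right to scale the VOC probabilities to the 24 planned participants (24 × 0.0082 = 0.2 to 24 × 0.1745 = 4.2), because 2 were enrolled. Infection is a weak example, since exclusion 11 bars active systemic infection within 14 days before dosing.

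The reply does not remove the mislabelling itself. Under the single-record reading, the stated rule calls on-drug worsening pretreatment and withholds the two conservative defaults, and no other section corrects it.

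**Conclusion.** The gap is real and small. SAP 6.1 has no worsening criterion, so a Screening-onset AE that increases in grade or becomes serious after the first dose, if kept under its original record, is flagged pretreatment and does not receive the defaults reserved for TEAEs. The effect stops there. For VOC, the expected number of participants exposed to the problem is at most about 0.02 to 0.35, on the assumptions of a constant rate across the range in inclusion 6 and durations of 3 to 7 days. The top of that range needs both participants to have 10 crises a year lasting 7 days each.

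The conclusion depends on the single-record reading, which the documents neither require nor exclude. The point is minor in consequence, but it should be fixed because a stated rule gives a wrong classification and the correction costs almost nothing.

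**What to change.** Reword SAP 6.1 so that a TEAE is an AE that starts on or after the first dose, or one that starts before the first dose and increases in CTCAE grade or becomes serious on or after it, in both cases within the existing 100-day limit. Restrict the pretreatment label to AEs that start before the first dose and do not worsen in this way. Add the date of worsening to the AE listing, or state that such worsening is entered as a new AE with its own start date and linked to the original.

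The cost is a sentence or two in the SAP and one listing column or eCRF completion note. A few more events may be flagged as treatment-emergent. With 2 participants, every Screening-onset AE can be checked by hand against source.

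While that text is open, note a separate effect of the residual clause: an AE starting after Day 185 (last dose on Day 85) is also called pretreatment, although the endpoint runs through Day 211. Such events need a label of their own.

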4. STATISTICAL ANALYSES

4.1. General Considerations

All analyses will be performed using Statistical Analysis Software[®] (SAS[®]) Version 9.4 or higher (SAS Institute Inc., Cary, NC, USA) or other validated statistical software.

Baseline is defined as the last nonmissing observation before the first dose of the study intervention.

Treatment Period is 12 weeks for Cohorts 1 and 2. Follow-up Period is 18 weeks after the last dose or may be longer if CAP activity is below the normal range or 80% of the baseline value, as defined in the protocol.

Study and participant characteristics (e.g., disposition, demographics and baseline characteristics, medical history, and protocol deviations) are described in Section 6.2.

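### SAP 6.1 closes the TEAE window 26 nominal days before the Day 211 primary safety endpoint ends and has no post-treatment class for a fully dated later AE

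*SAP*

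**What the plan says.** The definition is in SAP 6.1. A TEAE starts on or after the first dose "and up to 100 days after the last dose of the study intervention". Rules for missing or partial start dates follow:

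- A known later year: "If the start year is after the year of the first study intervention dose, then the AE is treatment emergent".
- The same year as the first dose: the AE is treatment emergent if the month is missing, or if "the start month is present and is the same or after the month of the first study intervention dose".
- No date at all: "If the start date is completely missing, then the AE is treatment emergent".

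The list closes with "All other AEs are considered pretreatment AEs". SAP 6.1 also fills in missing values, but for TEAEs only. A missing relationship counts as related, and "Missing severity for TEAEs will be counted as Grade 3".

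The time frame is set elsewhere. SAP Table 1 (section 1.1) gives the primary endpoint as TEAE and SAE incidence, examinations, vital signs, laboratory and "electrocardiogram results through Day 211 (Cohorts 1 and 2"). SAP 4.1 states: "Follow-up Period is 18 weeks after the last dose or may be longer if CAP activity is below the normal range". Protocol 8.3.1 collects AEs and SAEs from consent to the last follow-up visit. SAP 4.2.1 marks TEAEs in the AE listing by the SAP 6.1 definition. The protocol uses the term TEAE (for example in 9.4.3) but sets no window for it.

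**The concern.** The endpoint table and the derivation rule cover different periods. The endpoint counts TEAEs to Day 211, but the rule that decides what a TEAE is stops earlier. The point is that the two SAP statements disagree, not that 100 days is wrong in itself.

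Two further faults follow from the wording. First, there is no post-treatment class. Read literally, a fully dated AE that starts after the window becomes a pretreatment AE, which is plainly untrue. If the closing sentence is taken to finish only the missing-date rules, that AE has no class. Second, the flag depends on how complete the date is, because only fully dated events meet an upper limit.

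The uncovered stretch includes the nominal Day 211 visit, the only follow-up visit in protocol Table 6 with a full physical examination, and one that also has laboratory tests and triplicate ECGs. A clinically significant abnormality first found and dated there would not be flagged. What is at stake is the accuracy of the TEAE flag in the AE listing, together with the two missing-value rules that depend on it.

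**Working it through.** **The plan's own figure.** Protocol 1.1 gives 84 treatment days and 126 follow-up days: Day 1 + 84 + 126 = Day 211, as stated.

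**Last scheduled dose (SAP Table 2).**
- Cohort 1, 13 weekly doses: 1 + 12 × 7 = Day 85.
- Cohort 2, 4 doses every 4 weeks: 1 + 3 × 28 = Day 85.

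**Nominal gap.**
- Follow-up: 211 − 85 = 126 days, or 18 weeks, in agreement with SAP 4.1.
- TEAE window end: 85 + 100 = Day 185.
- Gap: 211 − 185 = 26 days; 26/126 = 20.6% of follow-up.
- Of the follow-up visits on Days 99, 127, 155, 183 and 211, only Day 211 falls after Day 185.

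**Early discontinuation.** Administrative Change Letter #3 puts the first follow-up visit (labelled Day 99) 14 ± 3 days after the actual last dose and continues the Table 6 schedule through Day 211. Nominal follow-up is 14 + (211 − 99) = 126 days, so the gap is again 126 − 100 = 26 days. For Cohort 2:

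| Last dose | Window end (last dose + 100) | Nominal final visit (last dose + 126) | Gap |
|---|---|---|---|
| Day 1 | Day 101 | Day 127 | 26 days |
| Day 29 | Day 129 | Day 155 | 26 days |
| Day 57 | Day 157 | Day 183 | 26 days |
| Day 85 | Day 185 | Day 211 | 26 days |

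**Allowing for visit windows** (Day 85 is ±1 day in Cohort 1 and ±3 in Cohort 2; Day 211 is ±3).
- Cohort 1, dosing completed: 208 − (86 + 100) = 22 to 214 − (84 + 100) = 30 days.
- Cohort 2, dosing completed: 208 − (88 + 100) = 20 to 214 − (82 + 100) = 32 days.
- Early discontinuation, final visit counted from the last dose: (123 to 129) − 100 = 23 to 29 days.
- Early discontinuation, final visit counted from the actual first follow-up visit: (11 + 112 − 3) − 100 = 20 to (17 + 112 + 3) − 100 = 32 days. The documents do not say which count applies.

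The gap stays positive throughout. Complement Activity Follow-up visits after Day 211 would lengthen the uncovered period.

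**Effect of date completeness (hypothetical dates).** Take a first dose on 20 Apr 2023.
- Day 85 is 13 Jul (+84 days), the window ends on 21 Oct (+100 days, Day 185), and Day 211 is 16 Nov (+26 days).
- An AE dated 8 Nov 2023 is on Day 203, 203 − 85 = 118 days after the last dose. It is not a TEAE.
- The same AE recorded only as Nov 2023 has the year of the first dose and a later month, so it is a TEAE, although all of November lies after 21 Oct.

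**A date pattern with no rule.** A known month with a missing year fits none of the partial-date bullets. It reaches only the closing pretreatment sentence.

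**The case against.** The two statements can be read together: AEs are observed through Day 211, and TEAEs are a defined subset of them. Only the TEAE component of the endpoint is touched. SAEs are named separately, and laboratory, vital-sign, examination and ECG results do not depend on the window. This narrows the point but does not remove it, because Table 1 gives TEAE incidence itself the Day 211 time frame. Nor does that reading supply a class for a late, fully dated AE.

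The case on impact is strong and stands. Two participants were enrolled (SAP 1.2), data are only listed (SAP 1), and summary statistics are withdrawn (SAP 4.5), so no TEAE incidence is calculated. All AEs are listed with their seriousness criteria (SAP 4.2.1). The documents do not show that either participant was followed beyond 100 days after the last dose. Listing specifications are in a separate Data Presentation Plan that is not available here, so whether a pretreatment label is printed is unknown. Flagging partially dated late events is the cautious direction. The protocol requires a causality assessment for every AE (10.3.3), so missing relationships should be rare.

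One objection concerns the remedy: a window that runs to the last follow-up visit could extend past Day 211 when complement follow-up continues. That is true, but such a window still contains the whole endpoint period and matches AE collection. Adding a post-treatment class avoids the question.

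**Conclusion.** The concern holds and is minor. SAP 6.1 leaves the last 26 nominal follow-up days (20.6% of 126) outside the TEAE window, although SAP Table 1 counts TEAEs through Day 211. As written, a fully dated AE in that period is called pretreatment, or has no class on the more generous reading, while the same event with its day missing is flagged as a TEAE. This is a stated rule that gives a wrong result, not merely absent detail.

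The 26 days assume a last dose on Day 85, or the 126-day schedule after early discontinuation; visit windows give 20 to 32 days. At most 2 participants are affected, through one flag in a listing, and no estimate changes. Confidence is high about the wording. Whether any recorded event falls in the gap cannot be told from the documents.

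**What to change.** Revise SAP 6.1 as follows:

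1. Define pretreatment AEs as those that start before the first dose, or whose partial start date or stop date places them before it. Add a residual rule that an AE whose partial date cannot place it before the first dose or after the window is a TEAE. This also covers a known month with a missing year.
2. Either extend the TEAE window to the last follow-up visit (at least Day 211), or keep 100 days, add a post-treatment class, and state that the TEAE part of the endpoint covers only that window.
3. Apply the chosen upper limit to partially dated AEs when the known year and month place the event wholly after it. In the example, Nov 2023 would be post-treatment if 100 days is kept.
4. If 100 days is kept, say whether the missing-relationship and missing-severity rules apply to post-treatment AEs.

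The cost is three to five sentences and one derivation flag, with no new data.
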